##### 3.1.1 Eovist® enhanced MRI

MRI will be performed in the Molecular Imaging Clinic. Pre contrast T1, T2 weighted scans with or without endorectal coil will be obtained through the prostate gland, bone metastasis or soft tissue metastasis (usually a lymph node) selected as the target lesion. Then 0.1 ml/kg Eovist® will be administered IV. Scans will be obtained immediately, 10, 20 and 60 minutes after injection using the same settings. Contrast enhancement ratios will be determined at each time point (Section 3.3).

##### 3.1.2 OATP1B3 Genotyping

Genotyping experiments will be performed using genomic DNA isolated from stored frozen serum using the QIAamp DNA blood mini-kit (Qiagen, Inc, Valencia, CA). This method has been previously utilized for the isolation of genomic DNA in the [name] laboratory [3, 4] and has resulted in DNA yields of approximately 50-400 ng/0.5ml of serum.

Genomic DNA will be amplified using *Taq* polymerase. Depending on the gene, single nucleotide polymorphisms in the CYP450 alleles will be identified using direct sequencing. [name] laboratory has previously published methods for genotyping the OATP1B3 alleles under study [3, 4].

All biosamples have been given a specimen code number on arrival in the laboratory. All further manipulation of the data is performed using the code number. Only named investigators will have access to this information, but most information will be stored and analyzed by the statistics section of the CCR.

### **3.1.3 Pathology**

#### **3.1.3.1 Surgical Pathology**

[figure not shown]
[figure not shown]
For the localized disease arm, biopsy specimens obtained from intraprostatic lesions or prostatectomy specimens will undergo standard preparation and sectioning in the Laboratory of Pathology for pathological diagnosis. The biopsy procedures for the localized disease arm will be part of standard of care.

For the advanced disease arm, biopsy specimens obtained from distant lesions will undergo standard preparation and sectioning in the Laboratory of Pathology for pathological diagnosis. The biopsy procedure for the advanced disease arm will be research biopsies and will be performed under imaging (ultrasound or CT) guidance.

#### **3.1.4 Immunohistochemistry**

Immunohistochemistry analysis will include exploratory assessment of OATP1B3 expression. Analyses will be performed on tumor from all specimens obtained and, will be performed at NIH. The [name] Lab has previously published immunofluorescence methods to detect OATP1B3 in prostate tissue sections isolated from men with benign prostatic hyperplasia, and prostate cancer [3]. The assay was able to distinguish between expressing and non-expressing tumors using a primary OATP1B3 antibody purchased from Santa Cruz Biotech. This will be used for IHC analysis. Moreover, we are currently developing better methods of detection in collaboration with [name] (University of Colorado Denver). We are also collaborating with [name] (University of Kentucky) who has recently published IHC methods using antibodies developed in-house. This is a topic which is still under investigation. The scope of collaboration with these groups will be limited to data exchange, but will not include sending out tissue samples.

### 3.2 Study Schema

**Figure 1: Study Schemas for localized and advanced disease arms.**

Note: Tissue samples must be obtained within ±20 weeks of Eovist® MRI

### **3.3 Study Drug Administration/Administration of Eovist®**

Under the supervision of PI or designated personnel, each subject will receive a single IV dose of Eovist® by bolus injection at a rate of approximately 2 ml/second at a dose of 0.1ml/kg. The injection will be followed by a 10-ml saline flush (sodium chloride IV infusion 0.9% w/v) over about 10 seconds.

The injection site will be evaluated before and after injection, to assess for the presence of signs of local irritation.

A member of the MIP clinical team will be in attendance during the injection. In the event of an emergency, such as an allergic reaction, immediate treatment will be initiated using emergency medication available in the Molecular Imaging Clinic. If the subject requires admission due to the severity of the reaction, the subject will be admitted to UOB, MOB or CCMD services for observation as the clinical situation dictates.

### **3.4 Dose Modifications**

If an adverse reaction is noted during the infusion, the infusion will be discontinued

### **3.5 Correlative Studies**

#### **3.5.1 Imaging Correlation**

A volume of interest (VOI) will be drawn over the target lesion in the baseline and in post-Eovist® injection MR images and the amount of contrast enhancement will be recorded by using dedicated image analysis software (MIM 5.4 Software, MIM Software Inc. Cleveland, OH, USA). Enhancement ratios [(signal enhancement after enhancement-signal enhancement before enhancement)/signal intensity before enhancement] will be calculated on pre and post-injection T1W MR images.

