### 1.2.3 OATP1B3 Transports Testosterone and affects clinical outcomes in CaP

Previous studies have demonstrated that single nucleotide polymorphisms (SNPs) in *SLCO* genes, which encode OATPs, can markedly alter testosterone transport efficiency. Recently, the [name] lab has specifically evaluated these SNPs and their association with androgen

transport. They showed that a common *SLCO1B3* GG/AA haplotype is associated with impaired testosterone transport and improved survival in patients with prostatic cancer [3]. The study examined (a) the *SLCO1B3* genotype in cancer cells as well as the uptake of testosterone by cells transfected with genetic variants of *SLCO1B3*; (b) the expression of OATP1B3 in normal prostate, benign prostatic hyperplasia, and prostatic cancer; and (c) the role of *SLCO1B3* haplotype on the clinical outcome of Caucasian patients with androgen-independent prostatic cancer. Cells transfected with wild-type (334T/699G) *SLCO1B3*, actively transported testosterone, whereas its uptake was impaired in cells transfected with a gene carrying both 334G and 699A single nucleotide polymorphisms. Approximately half of localized prostatic cancers over-express OATP1B3 compared with normal or benign hyperplastic tissue; patients with *SLCO1B3* 334GG/699AA haplotype showed longer median survival (8.5 versus 6.4 years;  $P = 0.020$ ) and improved survival probability at 10 years (42% versus 23%;  $P < 0.023$ ) than patients carrying TT/AA and TG/GA haplotypes. The common *SLCO1B3* GG/AA haplotype is associated with impaired testosterone transport and improved survival in patients with prostatic cancer [3].

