2.1.1.5 ECOG performance status  $\leq 2$

2.1.1.6 Serum creatinine within 3 weeks prior to Eovist MRI  $\leq 1.8$ mg/dl and estimated glomerular filtration rate (eGFR) must be  $>30$  ml/min/1.73m^2.

2.1.1.7 Patients must have normal liver function as defined below:

- total bilirubin  $< 2X$  normal institutional limits or  $>3.0$  mg/dl in patients with Gilbert's syndrome
- AST(SGOT) and ALT(SGPT)  $\leq 3$  X institutional upper limit of normal

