### **3.6.1.3 MR Imaging Period**

Prior to entering the MRI scanner the patient will answer the standard MRI safety checklist administered to all patients undergoing MRI in the Clinical Center to insure that it is safe to perform an MRI. The patient will be placed into the magnet in supine position and an intravenous line will be placed. A 32 channel cardiac coil will be used for MR imaging. An endorectal coil will be used for localized disease arm.

The following scans will be obtained:

- Scout view of the pelvis to check positioning of the cardiac coil.
- T1 weighted MRI of abdomen and pelvis.
- T2 weighted MRI of abdomen and pelvis.
- Total nominal time: 40 minutes +/- 5 minutes for setup and clean-up +/- 10 minutes in case any sequence needs to be repeated due to unforeseen events such as patient motion during imaging acquisition. At any given time the patient will be required to lie still for 5-7 minutes.

After completion of the pre-injection MRI scan, patient will have the Eovist® injection as detailed above in section [3.3](#). The patient will be assessed for adverse events 15 minutes post-Eovist® Injection and if they are stable, the same MR imaging protocol (except for the scout view) specified above will be performed immediately after injection and at approximately 10th, 20th and 60th minute time points after injection with the same MRI set up.

Following imaging acquisition, the data will be transferred to the clinical PACS system for storage.

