### **7.3 Efficacy Analysis**

#### **7.3.1 Primary Efficacy Analysis**

The primary objective of the study is to evaluate the uptake and retention of Eovist® in prostate cancers measured by the change of MRI parameter values between pre- and post-injection (section 3.5.1). Log-transformed MRI parameter values between pre- and post-injection will be compared by the paired t-test. If the distribution of log-transformed MRI parameter values is skewed, nonparametric paired Wilcoxon signed-rank test will be used for comparison.

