#### 10.2.6 Incompatibilities

Anionic drugs primarily secreted into the bile (such as rifampicin) may reduce the hepatic contrast enhancement and the biliary excretion of Eovist®.

The chemical structure of Eovist® is shown in Figure 2 below.

**Figure 2** Structure of Eovist®

Molecular formula: GdC23H28N3O11Na2

Molecular weight: 725.72

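### Measuring only the lesion shows that it enhances, not that tumour retains the agent; prespecified reference regions on the same images would help separate the two

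*Combined protocol and SAP*

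**What the plan says.** The primary objective (7.3.1) is to "evaluate the uptake and retention of Eovist® in prostate cancers measured by the change of MRI parameter values between pre- and post-injection". The measurement behind it is in 3.5.1: "A volume of interest (VOI) will be drawn over the target lesion in the baseline and in post-Eovist® injection MR images". The enhancement ratio divides the rise in lesion signal by that lesion's pre-contrast signal, and the ratios "will be calculated on pre and post-injection T1W MR images". Section 3.1.1 adds that "Contrast enhancement ratios will be determined at each time point", meaning immediately and at 10, 20 and 60 minutes.

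Section 7.3.1 compares log-transformed pre- and post-injection values by a paired t-test, or by a signed-rank test if they are skewed. Section 7.3.2 correlates lesion signal change with OATP1B3 expression in the late-stage subgroup. Neither section uses a reference region or a covariate for clearance.

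Three other places bear on interpretation:

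- Section 1.2.4 says the agent quickly enhances every vascular organ and structure. It says that, in the earlier work, expressing and non-expressing lesions were told apart at 20 minutes by persistent enhancement against washout.
- Section 1.2.3 states the biological premise as a comparison: "Approximately half of localized prostatic cancers over-express OATP1B3 compared with normal or benign hyperplastic tissue".
- Section 2.1.1.6 says "estimated glomerular filtration rate (eGFR) must be" above 30 ml/min/1.73m², with creatinine at most 1.8 mg/dl. Section 10.2.2 describes impaired elimination of gadolinium agents in relation to reduced GFR.

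**The concern.** Lesion signal after injection has two sources: agent held in tumour cells, and agent still in blood and interstitium. Only the first is retention. By the protocol's own account, the second is expected in any perfused tissue whatever its OATP1B3 status. A test of post against pre within the lesion cannot tell them apart, so a significant result would be open to over-interpretation as evidence of tumour retention.

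The second source also depends on how fast each patient clears the agent. If that differs between patients for reasons unrelated to the tumour, it adds noise to the correlation with OATP1B3 grade, or confounding if clearance happens to track stage or grade. With 10 or 15 patients per arm there is little room for either.

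**Working it through.** **1. The plan's own power figure.** Inputs from 7.4: n = 10, SD of the log signal ratio 0.25, 1.2-fold change, 5% level, stated power 83%. I used the exact paired t-test, two-sided, with 9 degrees of freedom and noncentrality √n × log(fold)/SD.

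- Log base 2: √10 × 0.263/0.25 = 3.33, power 84.1%. This agrees with 83% to within about one point.
- Natural log: √10 × 0.182/0.25 = 2.31, power 53.9%.

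The log base is not stated. Base 2 is the one that reproduces the plan's figure.

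**2. How often the planned test is positive with no retention.** Suppose the lesion holds no agent in its cells but shows a residual rise from circulating contrast. The size of that rise is an assumption. With n = 10 and SD 0.25:

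| Non-specific rise | Significant, log2 SD | Significant, natural-log SD |
|---|---|---|
| 1.05-fold | 12.6% | 8.6% |
| 1.10-fold | 34.3% | 19.1% |
| 1.15-fold | 62.3% | 35.2% |
| 1.20-fold | 84.1% | 53.9% |

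The test is working correctly here, because the signal really has changed. It is answering a question about enhancement.

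**3. How much circulating agent could differ with kidney function.** The documents give no half-life and no renal share, so both are assumed. Let h be the half-life at eGFR 90, f the renal share of clearance, and compare eGFR 35 with 90. Relative clearance is c = (1 − f) + f × 35/90. The fraction remaining at time t is 2^(−ct/h), so the ratio to the eGFR 90 patient is 2^((1 − c)t/h).

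- Central case, h = 1 h and f = 0.5: c = 0.5 + 0.5 × 0.389 = 0.694.
- At 20 minutes: 0.852 versus 0.794, ratio 1.07. At 60 minutes: 0.618 versus 0.500, ratio 1.24.
- Lowest case, h = 1.5 h and f = 0.3 (c = 0.817): ratios 1.03 and 1.09.
- Highest case, h = 0.75 h and f = 0.7 (c = 0.572): ratios 1.14 and 1.48.

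The excess in circulating agent is therefore about 3-14% at 20 minutes and 9-48% at 60 minutes.

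**4. What that means for lesion signal.** The excess scales only the non-specific part of the signal. If signal is linear in agent and non-specific enhancement is e of baseline, lesion signal changes by (1 + e × ratio)/(1 + e). With e = 0.20 at 60 minutes this is (1 + 0.20 × 1.24)/1.20 = 1.04, range 1.015 to 1.08. With e = 0.50 it is 1.08, range 1.03 to 1.16.

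**5. Effect on the OATP1B3 correlation.** Suppose a share s of the between-patient variance in late signal is clearance unrelated to OATP1B3 (assumed 25% or 50%). A true correlation r becomes r√(1 − s). Approximate power is Φ(atanh(r√(1 − s)) × √(n − 3) − 1.96), with n = 15 as in 7.1.

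- r = 0.70, s = 0: power 85%.
- s = 0.25: r = 0.61, power 68%.
- s = 0.50: r = 0.49, power 47%.

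Section 3.1 gives 10 rather than 15 advanced patients; power would then be lower throughout.

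**The case against.** The strongest reply is that serial imaging already addresses washout, because a ratio is planned at four post-injection times. This stands in part: early-to-late change within a lesion carries information that a single scan does not. But a lesion can lose signal slowly because its cells hold the agent or because the blood does. The lesion's own curve does not say which, and 7.3.1 does not specify an analysis of the curve.

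A second reply is that this is a pilot, that 1.1.3 makes the OATP1B3 correlation exploratory (7.3.2 calls it secondary), and that stored images could be measured later. That lowers the stakes. It does not help the primary objective, which names retention, and a reference region picked after the data are seen is less credible than one fixed in advance.

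A third reply is that no reference tissue is a clean control. This stands. Muscle need not match tumour perfusion or extracellular volume. The premise in 1.2.3 is over-expression relative to benign tissue, which does not mean that benign prostate has no transporter. Subtracting uninvolved prostate could remove real uptake.

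Some stronger readings do not hold:

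- **The 60-minute excess rivals the 1.2-fold target.** The 9-48% is circulating agent under assumed kinetics, near the eGFR floor and at the latest scan. The 1.2-fold figure is lesion signal. At the 20-minute point that the rationale relies on, the excess is 3-14%.
- **The liver limits let in slow eliminators.** Section 10.2.6 says certain anionic drugs "may reduce the hepatic contrast enhancement and the biliary excretion of Eovist". That concerns drugs, not raised AST or ALT, and nothing in the documents links the admitted AST/ALT range to slower elimination. Section 4 already asks that listed non-essential drugs be held, that antibiotics be finished, and that essential exceptions be noted.
- **Signal-scale drift biases the ratio.** Sections 3.1.1 and 3.6.1.3 keep the same settings and set-up, and the documents give no evidence of drift.

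**Conclusion.** The point holds as one of interpretation. The lesion-only measure and test can show that prostate cancers enhance after injection. They cannot by themselves show that tumour retains the agent, because the protocol itself says enhancement is not specific to OATP1B3. This conclusion rests on the text alone and needs no pharmacokinetic assumption.

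That clearance varies with kidney function across the admitted range is supported in direction by 10.2.2 and 2.1.1.6. Its size is not: every percentage in steps 3 to 5, and the non-specific rises in step 2, depend on the stated assumptions. The creatinine limit also narrows the admitted renal range to some degree.

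The sample-size arithmetic is not affected. The change is worth making because it is cheap and bears directly on the primary objective. The planned analysis need not be withdrawn.

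**What to change.** **Section 3.5.1.** Draw prespecified reference regions on the same images, before injection and at every time point: a blood-pool vessel and skeletal muscle in both arms. In the localized arm add uninvolved prostate as a descriptive comparison only, since it may itself express OATP1B3. State in advance how each region is placed.

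**Section 7.3.1.** Keep the planned lesion test. Beside it, report the lesion-minus-reference difference in log signal ratio at each time point, with confidence intervals. State that tumour retention will not be claimed from the lesion-only test alone.

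**Section 7.3.2.** Report the OATP1B3 correlation with the reference-corrected value as well as the raw one.

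**Cost.** No new scan, visit or patient is needed. Section 3.6.1.3 already specifies "T1 weighted MRI of abdomen and pelvis" before and after injection, so reference tissue should usually be in the field. The price is a little more reading time and some added noise from the reference regions. The correction will be only partial, because no reference will match tumour perfusion exactly, and the report should say so.

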#### **3.5.2 Pathologic and Imaging Correlation**

Standard of care biopsy is planned for subjects enrolled in the localized disease arm of this study. For patients enrolled in the advanced disease arm, the biopsies will be obtained for research purposes.

In case the new imaging agent shows an unexpected finding, this will be correlated with conventional imaging. The physicians of the patient will use best clinical judgment in determining whether a finding will influence the surgical procedure.

#### **3.5.3 Histological Correlations**

OATP1B3 expression will be confirmed by staining for OATP1B3 in tissue samples on an investigational basis. IHC analysis will be conducted by one NCI pathologist and will be based on grade of positivity (0 (no staining), 1 (weak staining), 2 (moderate staining) or 3 (strong staining)).

#### **3.5.4 Safety Assessments**

Safety assessments will be obtained during the course of the study are summarized in the Study Calendar (Section [3.6](#)).

### 3.6 Study Calendar

The timing of study events in the following descriptions is relative to the administration of EOVIST®.

Procedure	Screening a	Baseline b	MR imaging			Scheduled Post-MRI c
			Just prior to MRI	Pre-injection MRI scan	Post injection MRI scan	
Informed consent	X					
Study entry criteria	X					
Demographic information	X					
Medical history and concurrent diseases	X					
Prior/concomitant medications	X					
Injection site monitoring				X	X d	X
Vital signs	X	X			X e	
Acute Care Panel, Hepatic Panel, Mineral Panel, PSA, & CBC	X f					
OATP1B3 Genotype analysis	X g					
Biopsy specimen available for OATP1B3 expression	X h, i					
Intravenous line started			X			
Eovist® injection				X		
Adverse Event Monitoring			X	X	X	X
MR Imaging				X	X j	
Biopsy Procedure						X k, l
Prostatectomy						X m
OATP expression and Comparative Analyses						X

a: Within 21 days of administrations of Eovist®

b: The day of MR imaging until just prior to administration of Eovist ®

- c. Timing of events is relative to administration of Eovist®
- d: 5 minutes post-Eovist® injection
- e: At the end of all scanning
- f: Clinical blood sample assessments must be performed within 21 days prior to administration of Eovist®.
- g: Will be performed at [name] Lab.
- h: For the localized disease arm, existing pathologic tissue (obtained <20 weeks before Eovist MRI) will be screened to see if it can be linked to MRI visible lesion in the patient candidate for Eovist MRI. Otherwise the tissue obtained from image guided biopsy (standard of care) at NCI will be used for OATP1B3 expression.
- i: For the advanced disease arm, availability of the previously (<20 weeks) obtained clinically acquired tissue will be checked.
- j: Immediately, 10, 20, & 60 minutes post-Eovist® injection
- k: To be conducted within <20 weeks after Eovist® enhanced MRI
- l: This applies for the advanced disease arm and will be conducted from a soft tissue or metastatic bone lesion (measuring  $\geq 1.5\text{cm}$  in diameter).
- m: This applies for the localized disease arm and will serve as a source of tissue only if previously acquired biopsy (confidently linked to an MRI visible lesion) or image guided standard of care biopsy at NCI will not be available.

### **3.6.1 Study Periods**

#### **3.6.1.1 Screening Period**

A screening visit will be performed within 21 days before administration of Eovist®. Subjects will be permitted to continue taking any routine or necessary medication.

All subjects must satisfy all the eligibility criteria listed in Section [2.1](#). Signed and dated informed consent must be obtained from all subjects before any study-specific procedures are performed.

The following data will be collected:

- Date of birth
- Weight
- Height
- Prior and concurrent medications
- Medical history and concurrent diseases
- Results of screening tests: laboratory tests

Personal data (including contact information) will be collected with the subject's permission and only to the extent that is necessary for the purposes of the study. Blood samples for laboratory tests will be drawn. Vital signs (i.e., systolic and diastolic blood pressure, heart rate, body temperature, and respiration rate) will be recorded.

#### **3.6.1.2 Baseline Period**

The baseline period is defined as the day of MR imaging until just prior to administration of Eovist®. At baseline, concomitant medication and pre-administration events will be recorded.

A cannula (or indwelling catheter) will be placed preferably into an antecubital vein for blood sampling and imaging agent administration. Blood samples for serum biochemistry and hematology will be drawn. Vital signs (i.e., systolic and diastolic blood pressure, heart rate, body temperature, and respiration rate) will be recorded.

If the screening clinical blood sample assessments are performed within 48 hours of administration of Eovist®, they do not need to be repeated.

